9.0 Study Enrollment Procedures

Participating investigators are responsible for confirming the eligibility/ineligibility status of a potential study participant prior to enrollment. Since this trial requires the active participation of both thoracic

surgeons and radiation oncologists, a patient should be assessed by both specialists prior to being offered participation in the trial.

Potentially eligible patients will be offered voluntary participation in this trial by their participating physician. Patients will be given an informed consent form to review and will be contacted at a later date by trial personnel to answer any questions which may arise and to obtain written informed consent.

Patients who have consented to trial participation will then undergo all required pre-treatment investigations (if not already done) in a timely manner.

10.0 Treatment

Calypso Beacon Placement:

Calypso beacon placement will be performed using flexible bronchoscopy under general anesthesia or conscious sedation. The site of implantation will be localized using a combination of direct visualization, fluoroscopy, ultrasound and electromagnetic navigation bronchoscopy. Drs. [name] and [name] have received formal course training on the use of SuperDimension Navigational Bronchoscopy System for localization of lung nodules and directed bronchoscopic placement of implant devices. This will greatly facilitate accurate beacon placement. The bronchoscope will be advanced under direct vision into the targeted implantation site. Using navigational bronchoscopy and fluoroscopy the target implant sites will be identified and guide sheath placed through the bronchoscopy working channel. Through the guide sheath, the catheter with anchored beacon transponder will be directed to the implantation sites under bronchoscopic and fluoroscopic direction. The beacon transponders will be deployed until properly anchored in the appropriate peri-tumoral implantation sites. Satisfactory beacon placement will be verified using fluoroscopy. The anchored transponders are implanted in a triangle around the tumor target and are at least 1 cm but no more than 7.5 cm from each other. Although navigational bronchoscopy is recommended for beacon placement, conventional bronchoscopy with fluoroscopic guidance is also acceptable for beacon placement at the discretion of the attending thoracic surgeon in the event that navigational bronchoscopy is unavailable on the day of the beacon placement procedure.

Radiotherapy:

4-Dimensional CT simulation Scan: Patients will be simulated in the supine position and immobilized using a Vac-lok bag with arms raised above their heads and with legs on a knee rest for comfort. Patients will be free breathing with a relaxed tidal breathing pattern. The CT simulation scan will be performed using the Varian RPM system in order to produce 10-respiratory phase correlated CT data sets (4-DCT scan). Intravenous contrast is not required.

Co-registration of PET scan: For purposes of contouring the primary tumor, PET scan fusion is recommended but not mandatory.

Organ at Risk Delineation: The following organs at risk will be contoured on the CT_{average} dataset:

- 1) Normal Lung;
- 2) Esophagus;
- 3) Chest wall (within 5 cm of the PTV);

- 4) Ribs (within 5 cm of the PTV);
- 5) Heart;
- 6) Kidneys (if the tumor is a lower lobe tumor);
- 7) Ipsilateral brachial plexus (if located within 5 cm of the PTV);
- 8) Spinal Cord;
- 9) Proximal Trachea;
- 10) Proximal bronchial tree;
- 11) Aorta (if left sided tumor);
- 12) Vena Cava (if right sided tumor);
- 13) Liver (if tumor is located in the right lower lobe)
- 14) Nearest vertebral body, and the vertebral body above and below the nearest vertebral body.

For organ at risk contouring guidelines, radiation oncologists are encouraged to reference the RTOG 0236 trial protocol.

Target Volume Delineation:

The Gross Tumor Volume (GTV) will be delineated on all 10 respiratory-phase correlated CT datasets with the CT Hounsfield unit window level set to the “lung window” preset. Participating radiation oncologists are encouraged to cross-reference the pre-treatment investigations (Infused CT chest, PET scan, etc) in order to aid with the delineation of the GTV.

Internal Target Volume: Using the average CT dataset, the ITV will be generated using the Eclipse™ “accumulate structure” function incorporating the GTVs created on all 10 phase-correlated datasets.

Gating Window Internal Target Volume (ITV_{GW}): The ITV_{GW} will consist of a accumulated structure composed of the GTVs contoured on the end-exhalation phases of the breathing cycle. The end-exhalation phases will typically include the GTVs from the CT50, CT40, and CT60 phases of the 4DCT scan. Depending on the individual patient’s breathing pattern, the ITV_{GW} could also include the GTVs from CT30 and CT70 if necessary (this decision to include CT30 and CT70 needs to be approved by the study PI on a case-by-case basis).

Planning Target Volume expansion margins:

For Phase I of the study - 5 mm isotropic expansion of the ITV

For Phase II of the study - 3mm isotropic expansion of the ITV_{GW}.

Note: For patients treated in phase II of the study, If setup errors noted during the first fraction of treatment are greater than 3mm in size for more than 10% of the overall treatment time, then a larger, case-specific PTV margin will be applied for the remaining 2 fractions of the radiotherapy. Any enlargements to the PTV will be applied with the prior approval of the study PI.

Radiotherapy Dose Prescription: 54 Gy to 95% of PTV in 3 fractions.

Radiotherapy Dose Coverage: 99% of the PTV receives at least 90% of prescription dose

Timing of Fractions: A minimum of 40 hours should separate each fraction.

Radiotherapy treatment planning: SABR treatment plans will be calculated using the Varian Acuros dosimetric algorithm with inhomogeneity correction. Two co-planar, two-hundred and forty degree arcs of volumetric modulated arc therapy (VMAT) will be the default beam arrangement.

SABR Delivery: SABR will be delivered using the Varian Edge linear accelerator at the KIAM using 10MV flattening filter free photon beams using a dose rate of 2400 MU/min.

Gating Window: The end-exhalation phase (CT50) plus one phase directly preceding (CT40) and following (CT60) will be used as the gating window. CT30 and CT70 may also be included in the gating window.

Chemotherapy: Chemotherapy, immunotherapy, or mutation targeted therapies should be held at least 24 hours prior to the first fraction, and can be restarted 24 hours after the delivery of the last fraction.

Cone Beam CT-based (CBCT) Image Guidance: In phase I of the trial, cone beam CT scans will be performed daily in order to allow for initial image guidance of treatment setup using bony landmarks (vertebral bodies) and soft tissue (tumour). Calypso beacon data will be collected during phase I including inter-transponder geometry.

Calypso Guidance: In Phase II of the trial, calypso beacon data will be used to fine tune initial patient positioning and treatment delivery. The location data from the Calypso beacons will be captured by the Calypso array in order to assess inter-transponder beacon distance, as well as beacon geometric center location relative to the linear accelerator's isocenter. This position is used as the reference for Calypso to provide continuous monitoring. Calypso data will then be used for respiratory gating of the SABR treatment. CBCT imaging may also be performed to verify the soft tissue-beacon correspondence. CBCT images will be evaluated and may be used for patient repositioning if necessary.

Respiratory gating (phase I): For phase I of the trial, the respiratory gating signal will not be used to control the radiation beam delivery, however, Calypso transponder beacons will be used to provide location telemetry for quality assurance and data analysis purposes only.

Respiratory Gating (Phase II): The SABR radiation beam delivery will be gated using the Calypso transponder location data for phase II of the study.

OAR Tolerances (as derived from the RTOG 0618 protocol by Timmerman et. al.):

| Organ | Volume | Dose Constraint (Gy) |
|-----------------------------|---------------|-----------------------------|
| Spinal Canal | Point Dose | 19 Gy |
| | <0.35cc | 18 Gy |
| | <1.2cc | 10 Gy |
| Esophagus | Point Dose | 28 Gy |
| | <5cc | 15 Gy |
| Ipsilateral Brachial Plexus | Point Dose | 24 Gy |
| | <3cc | 22 Gy |
| Heart | Point Dose | 30 Gy |
| | <15cc | 24 Gy |

| | | |
|-------------------------|-----------------------|-------------------|
| Proximal Bronchial Tree | Point Dose <4cc | 30 Gy 14 Gy |
| Skin | Point Dose <10cc | 24 Gy 22 Gy |
| Ribs | Point Dose < 1cc | 30 Gy 24 Gy |
| Chest Wall | Point Dose < 30 cc | 30 Gy 20 Gy |
| Great Vessels | Point Dose <10cc | 35 Gy 30 Gy |
| Stomach | Point Dose <10 cc | 22Gy 15 Gy |
| Liver | >700cc | 15 Gy |
| Bilateral Normal Lung | See section below | See section below |
| Bilateral Normal Lung | V20Gy | <10% |

Dose Spillage and conformity:

High dose spillage: Any dose > 105% of the prescription dose should occur primarily within the PTV itself and not within normal tissues outside of the PTV. The cumulative volume of all tissues outside of the PTV receiving a dose of > 105% of the prescription dose should be no more than 15% of the PTV volume.

The falloff gradient beyond the PTV extending into normal tissue structures (especially the lungs) must be rapid in all directions and meet the following criteria which are dependent on the PTV volume as outlined in the table below: 1) The ratio of the volume of the 54 Gy isodose surface to the PTV volume should be less than 1.2 (see column two of the table below); 2) The ratio of the volume of the 30Gy isodose volume to the volume of the PTV must be no greater than the “ R_{30Gy} ” (see column three in the table below); 3) the maximum point dose at least 2 cm outside the PTV edge in any direction must be less than “ D_{2cm} ” (see column four in table below); and 4) the percentage of total lung volume receiving 20Gy or more (V20) should be less than 10% (see column five in table below).

| Maximum PTV Dimension (cm) | Ratio of Prescription Isodose Volume to the PTV | | Ratio of 30 Gy Isodose Volume to the PTV, $R_{30\text{ Gy}}$ | | Maximum Dose 2 cm from PTV in any Direction, $D_{2\text{cm}}$ (Gy) | | Percent of Lung receiving 20 Gy total or more, V_{20} (%) | | PTV Volume (cc) |
|----------------------------|---|---------|--|---------|--|-----------|---|-------|-----------------|
| | Deviation | | Deviation | | Deviation | | Deviation | | |
| | none | minor | none | minor | none | minor | none | minor | |
| 2.0 | <1.2 | 1.2-1.4 | <3.9 | 3.9-4.1 | <28.1 | 28.1-30.1 | <10 | 0-15 | 1.8 |
| 2.5 | <1.2 | 1.2-1.4 | <3.9 | 3.9-4.1 | <28.1 | 28.1-30.1 | <10 | 10-15 | 3.8 |
| 3.0 | <1.2 | 1.2-1.4 | <3.9 | 3.9-4.1 | <28.1 | 28.1-30.1 | <10 | 10-15 | 7.4 |
| 3.5 | <1.2 | 1.2-1.4 | <3.9 | 3.9-4.1 | <28.1 | 28.1-30.1 | <10 | 10-15 | 13.2 |
| 4.0 | <1.2 | 1.2-1.4 | <3.8 | 3.8-4.0 | <30.4 | 30.4-32.4 | <10 | 10-15 | 21.9 |
| 4.5 | <1.2 | 1.2-1.4 | <3.7 | 3.7-3.9 | <32.7 | 32.7-34.7 | <10 | 10-15 | 33.8 |
| 5.0 | <1.2 | 1.2-1.4 | <3.6 | 3.6-3.8 | <35.1 | 35.1-37.1 | <10 | 10-15 | 49.6 |
| 5.5 | <1.2 | 1.2-1.4 | <3.5 | 3.5-3.7 | <37.4 | 37.4-41.7 | <10 | 10-15 | 69.9 |
| 6.0 | <1.2 | 1.2-1.4 | <3.3 | 3.3-3.5 | <39.7 | 39.7-41.7 | <10 | 10-15 | 95.1 |
| 6.5 | <1.2 | 1.2-1.4 | <3.1 | 3.1-3.3 | <42.0 | 42.0-44.0 | <10 | 10-15 | 125.8 |
| 7.0 | <1.2 | 1.2-1.4 | <2.9 | 2.9-3.1 | <44.3 | 44.3-46.3 | <10 | 10-15 | 162.6 |

11.0 Potential Adverse Reactions:

The adverse effects associated with the use of the Calypso transponder beacons are similar in profile to other bronchoscopic procedures such as bronchoscopic biopsies or the implantation of inert gold seed fiducial markers.

Pneumothorax: The most commonly encountered adverse effect of fiducial marker placement is pneumothorax which has a risk of between 2 to 5 percent^{27,28} with the majority of these treated either conservatively or with a pigtail catheter for a day or two²⁴ after the procedure.

COPD Exacerbations: Exacerbations of emphysema or chronic obstructive pulmonary disorder (COPD) have been reported with a risk of up to 11 percent²⁹ in one small case series of 9 patients who had non-calypso beacons implanted. However, several much larger case series reported no COPD exacerbations^{24,27,28} whatsoever.

Beacon Migration: Beacon migration has been reported at a rate of 1%²⁴ using anchored calypso beacons which can lead to the expectoration of the migrated beacon.

Infection: There is a 1% risk of pulmonary infection in the tissue in close proximity to an anchored Calypso beacon²⁴.

Minor Bleeding: There is a small risk of minor local bleeding in the airway implanted with the transponder beacon with a risk similar to other bronchoscopic based procedures, however no pulmonary hemorrhages were reported in the case series using the anchored Calypso lung beacon²⁴.

MRI compatibility: Anchored Calypso beacons can be safely scanned using MRI with either a 1.5 or 3.0 Tesla static magnetic field with or a magnetic field gradient of up to 9.3 Tesla/meter without inducing any clinically significant displacement force or torque. An MRI image artifact may extend up to 2 cm from the anchored transponder, which is of no clinical significance for patients on this trial since, outside of research studies, MRI is not used in the routine diagnosis of intrapulmonary lesions.

Retrieval of Calypso Beacons:

If an unanticipated adverse effect occurs with a Calypso beacon and removal of the beacon is required, then the anchored beacons can be retrieved using a flexible bronchoscope and forceps similar to other endobronchial foreign body retrievals.

12. 0 Evaluation During and After Protocol Treatment

| | Baseline | 4DCT Sim* | Each SABR Fraction[¶] | 2 mo[#] | 6 mo | 12 mo | 18 mo | 2 yr | 3 yr |
|------------------------------------|------------------------|-----------------------------|--|------------------------------------|------------------------|-------------------------|-------------------------|--------------------|--------------------|
| History & Physical Exam | x | | | x | x | x | x | x | x |
| CT or MRI Brain | x | | | | | | | | |
| CT Chest & Abdomen | x | | | | x | x | x | x | x |
| PET Scan | x | | | | | | | | |
| Chest X-ray | | | | x | | | | | |
| Pulmonary | x | | | | x | | x | | x |

| Function Testing | | | | | | | | | |
|--------------------------------|---|---|---|---|---|---|---|---|---|
| 6 min walking test | x | | | | x | | x | | x |
| Medication Profile | x | | | x | x | x | x | x | x |
| CBC, Lytes, Bun, Cr | x | | | | | | | | |
| EORTC QLQ - LC13 | x | x | x | x | x | x | x | x | x |
| Toxicity Profile (CTCAE V 4.0) | x | x | x | x | x | x | x | x | x |
| Inter-beacon distance | | x | x | | | | | | |

Notes:

* 4DCT is to be performed no later than 4 calendar weeks after the date of beacon implantation

φ The first fraction of SABR is to start no later than 14 calendar days after the 4DCT simulation scan

the timing of all follow up evaluations are relative to the date of the last fraction of SABR.

13.0 Statistical Considerations:Descriptive characteristics:

Baseline patient, tumor, and treatment characteristics will be summarized using standard descriptive statistics as summarized in the table below.

| Patient Factors | |
|--|---------------------------|
| Age | Mean & Standard Deviation |
| Gender | Percentage |
| Comorbidity (Charlson Index) | Mean & Standard Deviation |
| Smoking History Category (Current smoker, previous smoker, never smoker) | Percentage |
| Smoking Pack-Year History | Mean & Standard Deviation |
| FEV1 (Liters) | Mean & Standard Deviation |
| Diffusion Capacity (%) | Mean & Standard Deviation |
| 6 Minute Walk Test (% of expected distance) | Mean & Standard Deviation |
| Tumor Factors | |
| T-stage (T1, T2) | Percentage |
| Tumor size (cm ³) | Mean & Standard Deviation |
| Tumor location (by lobe) | Percentage |
| Tumor Histology | Percentage |
| Treatment Factors | |
| GTV (cm ³) | Mean & Standard Deviation |
| PTV (cm ³) | Mean & Standard Deviation |
| Maximal observer tumor motion (cm) | Mean & Standard Deviation |
| Radiotherapy Dose Prescription (cGy) | Percentage |
| Radiotherapy Delivery Time Per Fraction | Mean & Standard Deviation |

Study Power:

Power calculations were conducted using the STATA 12.0 statistical software package (College station, Texas). Zhao *et al.*²² carried out dosimetric analyses of lung tumors undergoing SABR lung treatments with similar characteristics (T1-T2N0 NSCLC) to those which would be eligible for this study and found a median PTV volume of 62.9 cm³ (sd 43.6 cm³). Presuming similar sized tumor volumes as Zhao *et al.*, A sample size of 28 patients would yield a power of 0.92 to detect a 40% reduction in the mean PTV volume between standard ITV based SABR treatment as compared to gated calypso guided SABR, with an alpha value of 0.05 and using a 1-sided test for statistical significance.

Endpoints:

Percentage Change in PTV: For each participating patient, the PTV volumes will be calculated on the same 4DCT for standard ITV-based SABR treatment as well as the Calypso guided SABR treatment. The comparison of the PTV volumes will be calculated as follows:

$$\% \text{ change in PTV} = (\text{PTV}_{\text{standard SABR}} - \text{PTV}_{\text{Calypso Guided SABR}}) / (\text{PTV}_{\text{standard SABR}}) \times 100$$

This metric will be reported as a mean for the cohort with SD

Quality of Life Data: The mean EORTC QLQ – LC13 plus standard deviation will be tabulated in descriptive format for each evaluation time point.

Acute and Late Toxicity: The maximum grade of observed toxicity during treatment and follow-up will be tabulated in a descriptive format by adverse effect.

Percentage Change in Organ at Risk Dose Volume Metrics: For each organ at risk, percentage change in the dose-volume histogram metric of interest will be calculated as per the following example:

$$\% \text{ Change in Lung V20} = (\text{V20}_{\text{standard SABR}} - \text{V20}_{\text{Calypso Guided SABR}}) / \text{V20}_{\text{standard SABR}} \times 100$$

Pulmonary Function Test Results: Percentage change in pulmonary function test results (FEV1, DLCO, and 6 minute walk distance) will be calculated as per the following example at each follow-up time point:

$$\% \text{ Change FEV1} = (\text{FEV1}_{\text{baseline}} - \text{FEV1}_{\text{follow-up}}) / \text{FEV1}_{\text{baseline}} \times 100\%$$

Local Control: The RECIST³⁰ version 1.1 criteria will be used to assess the effect of SABR treatment on the local control of the tumor as per the following definitions:

| RECIST Outcome | Description |
|--------------------------|--|
| Complete Response (CR) | Disappearance of all target lesions |
| Partial Response (PR) | At least a 30% decrease in the sum of the LD of target lesions, taking as reference the baseline sum LD |
| Progressive Disease (PD) | At least a 20% increase in the sum of the LD of target lesions taking as reference the smallest sum LD recorded since the treatment started or |

| | |
|----------------------|---|
| | the appearance of one or more new lesions |
| Stable Disease (SD): | Neither sufficient shrinkage to qualify for PR nor sufficient increase to qualify for PD, taking as reference the smallest sum LD since the treatment started |

- 7) Survival: Progression-Free Survival (PFS), Cancer-Specific Survival (CSS), and Overall Survival (OS) will be estimated using the Kaplan-Meier method. For all three survival estimates, the survival period will be defined as the time from tissue diagnosis to progression event (for PFS), Cancer related death (CSS), death from any cause (OS) or time of censoring (due to loss to follow-up, or end of study).

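### The 5.5 cm row of the dose-spillage table gives a D2cm minor-deviation window of 37.4-41.7 Gy, 4.3 Gy wide where every other row is 2.0 Gy; 41.7 is most likely a slip for 39.4

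*Combined protocol and SAP*

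**What the plan says.** The dose spillage and conformity part of section 10.0 (Treatment) sets four criteria for how fast dose must fall off outside the PTV. The third is that "the maximum point dose at least 2 cm outside the PTV edge in any direction must be less than" the D2cm value listed for the PTV's size. The table that follows has eleven rows, for maximum PTV dimensions of 2.0 to 7.0 cm. For D2cm each row gives a limit for no deviation and a window for a minor deviation.

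The row in question, 5.5 cm, ends "<37.4 | 37.4-41.7 | <10 | 10-15 | 69.9". In order, these cells are the D2cm limit for no deviation, the D2cm minor window, the two lung V20 cells and the PTV volume in cc. The row above (5.0 cm) ends "<35.1 | 35.1-37.1 | <10 | 10-15 | 49.6" and the row below (6.0 cm) ends "<39.7 | 39.7-41.7 | <10 | 10-15 | 95.1".

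Nothing in the text explains a wider window at 5.5 cm.

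**The concern.** The 5.5 cm window is more than twice as wide as any other, and it shares its upper bound with the row below, although the no-deviation limits of those two rows differ by 2.3 Gy (39.7 - 37.4). That pattern fits a number copied from the adjacent row.

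What is at stake is consistent plan grading. Take a plan on the 5.5 cm row with a D2cm above 39.4 and up to 41.7 Gy. It exceeds its limit by more than 2.0 Gy and up to 4.3 Gy, and is graded minor. The same excess falls outside the minor window at every other PTV size. The organ dose table in section 10.0 would not necessarily catch such a plan, because normal lung has a V20 limit there but no point-dose limit.

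**Working it through.** **Inputs.** All D2cm figures come from the dose-spillage table in section 10.0. Width is the upper bound minus the lower bound of the minor window. The last column is width divided by the no-deviation limit, which is the largest excess still graded minor.

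| Max. PTV dimension (cm) | No deviation (Gy) | Minor window (Gy) | Width (Gy) | Largest excess graded minor |
|---|---|---|---|---|
| 2.0, 2.5, 3.0, 3.5 | <28.1 | 28.1-30.1 | 2.0 | 2.0/28.1 = 7.1% |
| 4.0 | <30.4 | 30.4-32.4 | 2.0 | 2.0/30.4 = 6.6% |
| 4.5 | <32.7 | 32.7-34.7 | 2.0 | 2.0/32.7 = 6.1% |
| 5.0 | <35.1 | 35.1-37.1 | 2.0 | 2.0/35.1 = 5.7% |
| **5.5** | **<37.4** | **37.4-41.7** | **4.3** | **4.3/37.4 = 11.5%** |
| 6.0 | <39.7 | 39.7-41.7 | 2.0 | 2.0/39.7 = 5.0% |
| 6.5 | <42.0 | 42.0-44.0 | 2.0 | 2.0/42.0 = 4.8% |
| 7.0 | <44.3 | 44.3-46.3 | 2.0 | 2.0/44.3 = 4.5% |

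**Can the printed figure be reproduced?** No. The rule *upper bound = lower bound + 2.0 Gy* returns ten of the eleven upper bounds exactly. At 5.5 cm it gives 37.4 + 2.0 = 39.4, not 41.7.

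**Which of the two bounds is out of line?** The row-to-row steps from 3.5 to 7.0 cm, in Gy, are:

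- No-deviation limit: 2.3, 2.3, 2.4, 2.3, 2.3, 2.3, 2.3.
- Minor upper bound as printed: 2.3, 2.3, 2.4, **4.6, 0.0**, 2.3, 2.3.
- Minor upper bound with 39.4 at 5.5 cm: 2.3, 2.3, 2.4, 2.3, 2.3, 2.3, 2.3.

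The limit of 37.4 fits its column, so the break lies in the upper bound alone.

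**Second route to the value.** The midpoint of the neighbouring upper bounds is (37.1 + 41.7)/2 = 39.4 Gy, the same as from the constant width.

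**Size of the discrepancy.** 41.7 - 39.4 = 2.3 Gy. With 39.4, the largest excess graded minor on this row would be 2.0/37.4 = 5.3%, between its neighbours at 5.7% and 5.0%.

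**Neighbouring column.** The minor windows for the 30 Gy isodose ratio are 0.2 wide in all eleven rows, including 5.5 cm, so the rest of the row is in sequence.

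**Could a plan fall on this row?** By size, a standard plan adds 5 mm on each side. A 3.5 cm tumour with 1.0 cm of motion along its long axis gives 3.5 + 1.0 + 2 × 0.5 = 5.5 cm. A phase II gated plan adds 3 mm on each side, so a tumour just under 4 cm gives at most about 4.0 + 2 × 0.3 = 4.6 cm before residual motion, and would need about 0.9 cm more to reach 5.5 cm. By volume, the planning figure of 62.9 cm³ in section 13.0 is nearest to this row (69.9 - 62.9 = 7.0 cc, against 62.9 - 49.6 = 13.3 cc for the 5.0 cm row). After the hypothesised 40% reduction it is 0.6 × 62.9 = 37.7 cm³, between the 4.5 cm row (33.8 cc) and the 5.0 cm row (49.6 cc).

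**The case against.** The strongest reply is that nothing stated in the protocol turns on this cell. The operative rule uses the no-deviation limit, which is intact at 37.4 Gy, so a plan in the disputed band is a deviation either way. The table has no grade beyond minor, no action follows from a grade, and no endpoint in section 7.0 or analysis in section 13.0 uses one. All of this stands.

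Exposure is also small. Phase II gated plans would seldom reach 5.5 cm, and the larger ITV-based plans are delivered only to the two phase I patients; in phase II they are comparators. A plan would also have to land between 39.4 and 41.7 Gy. Every organ point-dose limit in section 10.0 lies between 19 and 35 Gy, below even the 37.4 Gy limit. The band therefore matters only where the hottest point at 2 cm lies in lung, liver or another tissue without such a limit. This stands too, but it does not reduce the exposure to zero. Case-specific margin enlargement is allowed in phase II, the planning SD is 43.6 cm³, and no rule says how a PTV between rows is scored.

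Finally, 39.4 is an inference, and the documents cannot show whether the irregularity arose in this protocol or in a source table. That is a reason to confirm the value before changing it. It does not explain why one PTV size should be graded more leniently than the rest. A misread PDF is an unlikely cause, since 41.7 for 39.4 is not a one-character error and the row is otherwise in sequence.

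**Conclusion.** The concern holds, as a minor point. The D2cm minor window at 5.5 cm is 4.3 Gy wide against exactly 2.0 Gy in the other ten rows, and its upper bound is 2.3 Gy above the value the table's pattern implies. The irregularity itself is certain from the printed numbers. That the intended bound is 39.4 Gy rests on the assumption that this row follows the same rule as the rest; two routes give that figure, but it remains an inference.

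The consequence is limited to an over-lenient grade, at one PTV size, for plans with a D2cm above 39.4 and up to 41.7 Gy. How many plans that affects cannot be derived from the documents. The primary endpoint (percentage difference in PTV volume) and the power calculation are untouched.

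**What to change.** Have the physics team check the 5.5 cm D2cm minor window against the source of the table. If they confirm it, change 37.4-41.7 to 37.4-39.4 Gy, and re-score any plan already graded on that row. If the wider window is intended, add a sentence giving the reason.

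The same check can take in the 2.0 cm row, whose minor V20 window reads 0-15 where the other rows read 10-15. As it reads, it overlaps that row's no-deviation range of below 10%. This may only be an artefact of how the text was extracted from the PDF.

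The cost is one table cell and a look back at plans scored on the 5.5 cm row. Any such plan above 39.4 Gy would move out of the minor window. No data collection, sample size or analysis changes.
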